APPENDIX VIII: DESCRIPTION OF POINTS A AND B AND ICRU BLADDER/RECTAL DOSE REPORTING POINTS	82
APPENDIX IX: BLANK DIAGRAM ANTERIOR.....	84
APPENDIX X: BLANK DIAGRAM LATERAL.....	85
APPENDIX XI: COLLECTION AND SHIPPING INSTRUCTIONS FOR SERUM AND CERVICAL AND ANAL SWABS FOR EXPLORATORY OBJECTIVE SPECIMENS	86
APPENDIX XII: RADIATION THERAPY QUALITY ASSURANCE PROCESS.....	90

ABBREVIATIONS LIST

AAPM	American Association of Physicists in Medicine
ADCL	Accredited Dosimetry Calibration Laboratory
AIDS	Acquired immunodeficiency syndrome
AIN	Anal intraepithelial neoplasia
AMC	AIDS Malignancy Consortium
ANC	Absolute Neutrophil Count
AP/PA	Anterior Posterior/Posterior Anterior
BED	Biological Equivalent Dose
BEV	Beams Eye View
CBC	Complete Blood Count
CDDP	Cisplatin, cisplatinum, or cis-diamminedichloroplatinum(II)
CIN	Cervical intraepithelial neoplasia
CT	Computed tomography
CT A/P	Computed tomography of abdomen/pelvis
EBRT	External beam radiation therapy
EORTC	European Organization for Research and Treatment of Cancer
FIGO	International Federation of Gynecology and Obstetrics
FNA	Fine needle aspiration biopsy
GOG	Gynecologic Oncology Group
H&E	Hematoxylin and eosin staining
HAART	Highly Active Antiretroviral Therapy
HDR	High dose rate
HIV	Human Immunodeficiency virus
HPV	Human papilloma virus
HSIL	High-grade squamous intraepithelial lesion
IAEA	International Atomic Energy Agency
ICRU	International Commission on Radiation Units
IMRT	Intensity-Modulated Radiation Therapy
IROC Houston QA Center	Imaging and Radiation Oncology Core Houston QA Center
ITT	Intent to treat
IV	Intravenous
IVP	Intravenous pyelogram
LACC	Locally advanced cervical cancer
LDR	Low dose rate
Min	Minute
MRI	Magnetic resonance imaging
MTD	Maximum Tolerated Dose
NCI	National Cancer Institute
NNRTI	Non-Nucleoside Reverse Transcriptase Inhibitor
NSC	National Safety Council
NYHA	New York Heart Association
ODMC	Operations and Data Management Center
OHRP	Office for Human Research Protections

OSLD	Optically Stimulated Luminescent Dosimeter
PFS	Progression free survival
PI	Principal Investigator
QA	Quality Assurance
RCT	Radiation concomitant therapy
RT	Radiation therapy
RTOG	Radiation Therapy Oncology Group
SSD	Source-skin distance
SSDL	Secondary Standards Dosimetry Laboratories
SWOG	Southwest Oncology Group
TLD	Thermoluminescent dosimeter
WPRT	Whole pelvic radiation therapy

SITES PARTICIPATING IN THE STUDY

REGIMEN:	All participants with CD4 counts $> 200/\text{mm}^3$ ($0.2 \times 10^9/\text{L}$) will receive weekly cisplatin at a dose of $40 \text{ mg}/\text{m}^2$ concomitant with radiotherapy (external beam and brachytherapy). The first 3 participants with CD4 counts $\leq 200/\text{mm}^3$ ($0.2 \times 10^9/\text{L}$) will receive weekly cisplatin at a dose of $25 \text{ mg}/\text{m}^2$ with radiotherapy (external beam and brachytherapy). Based on review of the safety data from the first 3 participants, all other participants with CD4 counts $\leq 200/\text{mm}^3$ ($0.2 \times 10^9/\text{L}$) will receive weekly cisplatin at a dose of $40 \text{ mg}/\text{m}^2$ or no cisplatin with radiotherapy (external beam and brachytherapy). All participants will concomitantly receive combination antiretroviral therapy (ART) with an acceptable regimen that adheres to national guidelines for treatment of HIV infection.
PRIMARY OBJECTIVES:	
1) To determine if it is feasible to administer a regimen of cisplatin/RT in HIV-infected women with LACC on ART. This regimen is considered standard therapy for women with LACC who are not HIV infected. Feasibility will be assessed based on:
• Treatment completion proportion: the proportion of participants who complete the cisplatin/RT regimen• Screening ratio: the number of potential participants screened per enrolled participant• Availability proportion: follow-up completion proportion at 6 and 12 months2) To evaluate the safety and tolerability of concomitant chemoradiotherapy with cisplatin in HIV-infected women

EXPLORATORY AND FUTURE RESEARCH OBJECTIVES:

with LACC who are also receiving concomitant ART.

- 1) Determine the 1-year progression-free survival (PFS) of HIV-infected women with locally-advanced invasive cervical cancer (LACC) Stage IB, II, III, and IVA who receive weekly cisplatin concomitant with radiotherapy and ART.
 - Determine PFS in all registered participants, regardless of completion (intent to treat-ITT)
 - Determine the PFS in the subset of participants who complete the prescribed chemotherapy/radiotherapy
 - Compare PFS in these subjects with PFS of HIV-uninfected subjects as reported in the literature, stage for stage
- 2) To describe the effects of treatment on participants' CD4 counts, HIV viral load and concurrent AIDS-defining conditions
- 3) To describe cervical cancer recurrence patterns in HIV-infected participants with LACC defined as loco-regional and/or distant recurrences.
- 4) Determine 1-year overall survival and causes of death, (i.e., cancer-related, HIV-related, or other).
- 5) To evaluate the effects of weekly cisplatin concomitant with radiotherapy on adherence to ART
- 6) Collect serum and cervical and anal swab material for the following exploratory analyses:
 - a. To describe the distribution of HPV DNA types and HPV strain variants in cervical and anal swabs collected at baseline, prior to initiation of study treatment;
 - b. To assess the concordance between HPV DNA types and HPV strain variants detected in cervical and anal swabs collected at baseline, prior to initiation of study treatment;
 - c. To investigate the effect of study treatment on HPV persistence in cervical and anal swabs and its relationship to cervical cancer persistence or recurrence;
 - d. To describe the gene methylation profiles in cervical and anal swabs collected at baseline, prior to initiation of study treatment;
 - e. To assess the concordance between gene methylation

- profiles detected in cervical and anal swabs collected at baseline, prior to initiation of study treatment;
- f. To investigate the relationship between baseline gene methylation profiles and cervical cancer persistence or recurrence;
 - g. To measure serum antibody titers to HPV 16 and HPV 18 at baseline and on study, and to determine whether baseline titers or changes during therapy correlate with cervical cancer persistence or recurrence.

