4.1 Staging

4.1.1 Clinical Staging

Participants must have a chest x-ray and a CT of the abdomen and pelvis with contrast. Stage should be assigned and documented as permitted under FIGO staging criteria. The para-aortic lymph node region must be negative for metastasis by CT with contrast.

Additional procedures, such as IVP, ultrasound, cystoscopy, proctoscopy, or barium enema may be performed at the discretion of the investigator.

4.1.2 All participants with cancer confined to the pelvis (Stages IB2, IIA, IIB, IIIB, IVA) will receive pelvic irradiation and concurrent cisplatin as outlined below.

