9.0 EVALUATION CRITERIA

9.1 Outcome Measures

The major parameters of the outcome measures are feasibility. Also, we will determine the safety and tolerability of concomitant chemoradiotherapy with cisplatin in HIV-infected women with LACC who are also receiving concomitant ART.

- 9.1.1 Treatment completion proportion is the proportion of subjects who enroll and complete the cisplatin/RT regimen.
- 9.1.2 Screening ratio is the number of potential participants screened per enrolled participant
- 9.1.3 Availability proportion is the follow-up completion proportion at 6 and at 12 months.
- 9.1.4 Safety and tolerability will be evaluated through tracking the number of dose delays, dose reductions, missing doses, and compliance

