11.0 STATISTICAL CONSIDERATIONS

11.1 Statistical Analysis Plan

Treatment completion rate will be estimated as proportion of all women who complete cisplatin of those who initiate cisplatin treatment. The binomial proportion and its 95% confidence interval will be used to estimate the treatment completion rate.

The screening ratio will be estimated as the number of patients screened divided by the number of patients enrolled on the study. The Poisson rate and its 95% confidence interval will be used to estimate the screening ratio.

The Kaplan-Meier method will be used to describe the progression-free survival (PFS) and overall survival (OS). We will generate KM curves for Stage I/II participants as well as Stage III/IV participants. The stratified log-rank test will be used to evaluate the association of HAART use, node positivity including enlarged pelvic nodes, stratified for stage. Those factors that are significantly associated with PFS and OS will be incorporated into a proportional hazards model. The one-year PFS and OS will be estimated using the cumulative proportion progression free (for PFS) or surviving (for OS) and its 95% confidence interval.

Frequency tables will be used to summarize the occurrences of adverse events by severity grade. Frequencies of specific adverse events will be tabulated.

Toxicity assessment: All toxicities will be reported on standard case report forms at visits and graded by NCI CTC v4.0. There will be standard dose reduction schedules. All dose delays, dose reductions, and missing doses will be tracked via CRFs during therapy. These will be tabulated and reported as rates.

Adherence assessments are planned weekly during cisplatin therapy and at the end of protocol therapy. Participants will be considered inadherent to ARV if they report missing doses on more than one adherence assessment. The proportion of participants who were inadherent to ARV during protocol therapy will be estimated using the binomial proportion and its exact 95% confidence interval.

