11.2 Sample Size Considerations

The primary outcome measure for this trial is treatment completion rate. A treatment completion rate of 70% or above would be sufficient to consider this regimen for further study. To test the null hypothesis that the treatment completion rate is 0.50 against the alternative that it is 0.70 at the one-sided 0.0510 level with 0.90 power will require 38 evaluable patients. To allow for potential 15% dropout, 45 patients will be enrolled in the study.

We will recruit 45 participants from the AMC core sites in Africa over an estimated 2 year period of time and have a minimum of 1 year of follow-up. We anticipate that at least 50% of recruited participants will be Stage 3 and 4. This will be helpful in stratified analyses by stage and node positivity.

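### Low-CD4 women given radiotherapy without cisplatin are non-completers under 9.1.1 but outside the denominator under 11.1, so the primary completion rate has two values if that path opens

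*Combined protocol and SAP*

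**What the plan says.** - **Study Synopsis, Regimen.** Participants with CD4 above 200 receive weekly cisplatin with radiotherapy. The first three with CD4 of 200 or below receive a lower cisplatin dose. After a safety review of those three, later low-CD4 participants receive full-dose cisplatin "or no cisplatin with radiotherapy (external beam and brachytherapy".
- **Section 9.1.1.** "Treatment completion proportion is the proportion of subjects who enroll and complete the cisplatin/RT regimen". The denominator is women who enroll.
- **Section 11.1.** "Treatment completion rate will be estimated as proportion of all women who complete cisplatin of those who initiate cisplatin treatment". The denominator is women who start cisplatin.
- **Section 11.2.** "The primary outcome measure for this trial is treatment completion rate", and "A treatment completion rate of 70% or above would be sufficient to consider this regimen for further study". The test sets a null rate of 0.50 against an alternative of 0.70, and its size is stated thus: "at the one-sided 0.0510 level with 0.90 power will require 38 evaluable patients". The step from 38 to 45 allows for 15% dropout and nothing else.
- **Section 4.1.2.** All participants with cancer confined to the pelvis "will receive pelvic irradiation and concurrent cisplatin as outlined below".
- **Section 6.2.2.** If two or more women at a dose level have a dose-limiting toxicity, no more are added at that level or a higher one. A woman with such a toxicity at Dose Level -2 stops cisplatin and continues radiotherapy alone. The section does not say that later enrollees are given radiotherapy alone.

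No section says how a woman given radiotherapy alone from the start is scored, whether she is evaluable, or whether she is replaced.

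**The concern.** A woman treated without cisplatin under the synopsis has not dropped out or refused; the omission is part of her assigned treatment. The two definitions of the primary endpoint nevertheless treat her in opposite ways.

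Under 9.1.1 she lowers the completion rate however well she finishes radiotherapy, so protocol-assigned omission is mixed with failure to complete. Under 11.1 she disappears. The rate then describes only women who started cisplatin, while the feasibility objective in 2.2.1 speaks of HIV-infected women with locally advanced disease on ART, without a CD4 limit.

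The rate drives a go/no-go decision at 70%. The trial is open-label with a single arm, so a denominator left open could be chosen after the results are visible.

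**Working it through.** **1. The plan's own figures.** Inputs from 11.2: null rate 0.50, alternative 0.70, power 0.90, one-sided alpha printed as 0.0510. The one-sample formula is n = [(z_alpha·√(0.50·0.50) + z_power·√(0.70·0.30)) / 0.20]².

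- Alpha 0.0510: [(1.635·0.5 + 1.2816·0.4583)/0.20]² = 49.3, so 50 women.
- Alpha 0.10: [(1.2816·0.5 + 1.2816·0.4583)/0.20]² = 37.7, so 38 women.
- Dropout: 38/(1 − 0.15) = 44.7, so 45 women.

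The 38 matches alpha 0.10, not 0.0510. The printed value may be a merged edit or a text-extraction artefact. That is a separate matter, so both levels are used below.

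**2. Baseline with no radiotherapy-alone women.** The exact binomial rule is the smallest count whose null tail probability does not exceed alpha.

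| n | Alpha 0.0510: rule, power at 0.70 | Alpha 0.10: rule, power at 0.70 |
|---|---|---|
| 38 | at least 25, 0.77 | at least 24, 0.86 |
| 45 | at least 29, 0.84 | at least 28, 0.90 |

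Losses due to this point should be read against these values, not against the stated 0.90.

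**3. Both definitions with k radiotherapy-alone women.** Assumptions: k is assumed, since the documents give no low-CD4 share; all 45 women are counted; there is no dropout; every woman assigned cisplatin starts it; true completion among them is 0.70.

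- 9.1.1: expected rate = 0.70·(45 − k)/45; power = P[Bin(45 − k, 0.70) ≥ 29 or 28].
- 11.1: expected rate = 0.70 on n = 45 − k, with the cutoff reset for that n.

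| k | 9.1.1 expected rate | 9.1.1 power, alpha 0.0510 | 9.1.1 power, alpha 0.10 | 11.1 n | 11.1 power, alpha 0.0510 | 11.1 power, alpha 0.10 |
|---|---|---|---|---|---|---|
| 0 | 70% | 0.84 | 0.90 | 45 | 0.84 | 0.90 |
| 3 | 65% | 0.63 | 0.74 | 42 | 0.84 | 0.90 |
| 6 | 61% | 0.35 | 0.48 | 39 | 0.74 | 0.91 |
| 10 | 54% | 0.065 | 0.13 | 35 | 0.77 | 0.87 |

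The 11.1 powers do not fall steadily because the exact cutoff moves in whole women.

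**4. One data set, two answers.** Take k = 10, with 25 of the other 35 women completing.

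- 11.1: 25/35 = 71%. This is above 70% and meets the exact cutoff for n = 35 at either alpha (23 or 22).
- 9.1.1: 25/45 = 56%. This is below 70% and misses the cutoff at either alpha (29 or 28).

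To reach 70% of 45 under 9.1.1 (31.5, so 32 women), 32 of the 35 would have to complete, or 91%.

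**The case against.** The strongest reply is that each definition is a legitimate feasibility measure. If cisplatin cannot be offered to low-CD4 women, that is itself a failure to deliver the regimen, so 9.1.1 is defensible for all comers. The 11.1 rate is a valid completion rate conditional on starting. This stands. A reader might infer that neither score measures feasibility, and the documents do not support that. The defect is that both are written down for one primary endpoint, they answer different questions, and nothing says which governs.

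Three other stronger readings also go too far:

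- **That the run-in rule assigns later women to radiotherapy alone.** The option appears in the synopsis. Under 6.2.2 no more women are added at the failed level or above, and 6.2.1 holds low-CD4 enrollment pending review. Low-CD4 accrual might simply close, leaving no such women. For the same reason, the chance that 6.2.2 stops at Dose Level -2 (0.29 or 0.51 at assumed toxicity rates of 20% or 30%) is not the chance that this path opens. Moreover, at assumed toxicity rates of 15% to 30%, 57% to 67% of that stopping probability comes from the branch with four to six run-in women, so fewer remain to be affected than if the run-in stayed at three.
- **That these women certainly stay in the primary analysis.** The synopsis calls them participants, so counting them among the 45 is reasonable. But evaluable is undefined, and they could be placed among the seven not expected to be evaluable.
- **That 11.1 removes the whole low-CD4 group.** Run-in women started cisplatin, so they remain in its denominator, and those who stop early count as non-completers. Only later women never given cisplatin leave.

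**Conclusion.** The point holds in conditional form. If any participant is given radiotherapy without cisplatin, 9.1.1 and 11.1 yield different primary completion rates and can give opposite go/no-go conclusions.

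Most of the statistical damage falls on 9.1.1: six such women roughly halve its power at either alpha. Under 11.1 the power loss is modest, and the problem is scope: the rate says nothing about later low-CD4 women not offered cisplatin.

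The sizes rest on an assumed number of such women, 70% completion among the others, all 45 counted and no dropout. The conflict between the definitions rests on none of these. It should be settled before results are known.

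**What to change.** 1. Use one primary denominator in 9.1.1, 11.1 and 11.2: enrolled women assigned a cisplatin-containing regimen. Count those who never start or who stop cisplatin early as non-completers, and define evaluable to match.
2. Report separately the radiotherapy completion proportion among women assigned radiotherapy alone, and the number and share of women with CD4 of 200 or below not offered cisplatin. This is needed because the proposed denominator, like 11.1, leaves these women out.
3. Report completion by CD4 stratum and the all-enrolled proportion as supporting results.
4. If the no-cisplatin path is used, state that the go conclusion does not extend to women with CD4 of 200 or below, and restate the number analysed and the power.
5. Reconcile the synopsis, 4.1.2 and 6.2.2 on whether later low-CD4 women are enrolled and what they receive. This review does not say which should govern.

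The cost is protocol and SAP wording plus one table. If the path opens, the feasibility claim is narrower. Low-CD4 run-in women would still contribute to the pooled rate, which is why the CD4 breakdown must accompany it.

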1.0 INTRODUCTION

The standard of care for the treatment of locally-advanced cervical cancer (LACC) is concurrent chemoradiotherapy using cisplatin as the chemotherapeutic radiosensitizing agent. This regimen is the current standard of care based on multiple randomized, controlled trials (RCT) that showed improved efficacy when cisplatin was added to radiation therapy, even in high-risk patients who have histologic evidence of metastatic disease to pelvic and/or para-aortic lymph nodes (1-3). Evidence from 5 randomized clinical trials (RCTs) (GOG 85, RTOG 9001, GOG 120, SWOG 8797, GOG 123) prompted an NCI alert in February 1999 that recommended consideration of concomitant chemoradiotherapy for all patients with cervical cancer (4). A Cochrane database review of 19 RCTs in LACC confirmed improvement in overall survival and progression free survival (PFS) (5). The addition of chemotherapy also appears to afford higher objective response rates; however, it was noted that the survival increase did come at the cost of significant hematologic and gastrointestinal toxicity in subsets of LACC patients.

Like many AIDS-related malignancies, HIV-associated invasive cervical cancer appears to have decreased in incidence in the U.S. due to an understanding of the need for aggressive treatment of precancerous cervical lesions in the setting of HIV. Nevertheless, LACC in HIV is still a major problem worldwide. None of the pivotal RCTs proving the benefits of adding cisplatin to radiation therapy included HIV-infected women with LACC, so efficacy data in the setting of HIV are limited to retrospective analyses. Acute and long term toxicity data in LACC in the setting of modern antiretroviral therapy (ART) do not exist for two main reasons: 1) HIV-associated cervical cancer is rare in developed countries, and 2) in countries which have a large number of HIV-associated cervical cancer patients, modern ART was not regularly used until recently due to lack of access or financial means to pay for the medications.

Optimal cisplatin-based treatments have evolved since the early studies in the mid-1980s. Many of the early regimens consisting of cisplatin alone or in combination with other chemotherapeutic agents, such as 5-FU or hydroxyurea, were inpatient regimens that required intravenous (IV) hydration and mannitol continuously for 5 days (2, 3, 6, 7). Because of the ease of weekly dosing and the lower cost of outpatient administration, a trend to use outpatient weekly cisplatin (40 mg/m^2) emerged despite no RCT showing efficacy or toxicity equivalency to inpatient 5-day regimens (8,9). Other dosing regimens commonly used worldwide include cisplatin 75 mg/m^2 every 3 weeks for 2 cycles during radiotherapy (unpublished data, but used in South Africa and many Southeast Asian sites per personal communications at the State of the Science of Cervical Cancer Meeting, Manchester, England, 2009).

Unfortunately, little is known about the effects of ART on standard treatments for cervical cancer with regards to drug-drug interactions because HIV-infected women with LACC have been typically excluded from clinical trials (10). Many antiretroviral agents are notorious for causing drug-drug interactions. Co-administration of standard cytotoxic and targeted therapies with ART could impair the efficacy or increase the toxicity of these combined therapies. Additionally, HIV-infected patients with cervical cancer often have a poor nutritional status while they are undergoing high-dose pelvic radiation therapy. While there are no prospective studies in cervical cancer, the combination of factors that causes poor marrow reserve in other AIDS malignancies can lead to increased toxicity and reduced efficacy in HIV-infected women with cervical cancer compared with their non-HIV-infected counterparts (11). Also, while

standard dosing for weekly cisplatin is 40 mg/m² when given concurrently with RT, there are some data that suggest that this weekly dose might be too high for some patient populations, especially in Africa (21).

- 1) Concomitant chemoradiotherapy with cisplatin-containing regimens show superior efficacy for LACC when compared with radiotherapy alone in HIV-uninfected women.
- 2) This has not been proven in the setting of HIV, where cervical cancer is common particularly in regions of the world that do not have robust screening programs. In fact, there are limited data regarding HIV-associated LACC in the literature primarily due to the exclusion of these women from the majority of clinical trials. Also, cisplatin-containing regimens have not been studied in cohorts of women on HAART throughout their treatment.
- 3) The optimal dosing for cisplatin when combined with radiation has not been prospectively tested in the setting of differing degrees of viremic suppression with HIV infection in patients receiving ART. There is evidence to suggest there are differences in efficacy and toxicity with lower doses in HIV-uninfected women with LACC (21).
- 4) AMC-081 represents the initial clinical trial of cervical cancer in HIV-infected individuals on ART to be conducted in a resource-limited environment.

- 5) AMC-081 represents the first AMC cervical cancer trial and one of its first international trials. Hence, this is a feasibility study to assess the treatment completion rate, screening rate and safety of a regimen that is standard for women with cervical cancer who are not HIV infected.
- 6) This trial will also integrate the Imaging and Radiation Oncology Core Houston Quality Assurance Center and will provide important information for QA/QC for future AMC trials requiring RT in Africa.
- 7) This trial will provide estimates of treatment completion rates, screening rates, follow-up rates and preliminary estimates of response rates that will inform development of planning a phase II trial that will evaluate efficacy endpoints.
- 8) AMC-081 will provide the first prospectively-collected data on HPV DNA types and strain variants, gene methylation patterns, and HPV serology in HIV-infected women with invasive cervical cancer in Africa and, in a preliminary way, will provide important information on their potential utility as markers for persistence or recurrence in HIV-associated cervical cancer.

